8.1.8 Interim Analyses

An interim analysis will be conducted when the last subject completes the Week 28 visit and all data pertaining to Week 28 and earlier are cleaned. For this analysis all Week 16 efficacy endpoints will be analysed, and all safety as well as pharmacokinetic and anti-immunogenicity data received by cut-off date will be analysed. Another interim analysis will be conducted when the last subject completes the Week 52 visit. The analyses will be performed for the efficacy endpoints until Week 52, as well as all safety and pharmacokinetic and immunogenicity data received by cut-off date.

Additional interim analysis may be performed if deemed necessary for regulatory purpose.

8.1.9 Handling of Missing Data

Every effort should be made to collect complete data at all visits.

In addition to the as-observed analysis, the following rules will be used to impute for missing data:

- For continuous endpoints, LOCF (Last Observation Carried Forward) will be used to impute missing values
- For all binary endpoints (i.e., endpoints that are either 1 (subject responded) or 0 (subject did not respond)):

- If no assessment after that visit*, then impute as failure (NRI [No Response Imputation])
- If there are assessments at visits* before and after, only impute as success if both visits are successes; else impute as failure

* Subjects that take prohibited medications to treat Psoriasis will be treated the same as those that discontinued from the trial – i.e., subsequent visits following start of prohibited medication will be considered as failure for binary endpoints.

8.2 Determination of Sample Size

The sample size is not estimated based on powering for any hypothesis testing. There are only approximately 1600 and 40000 Japanese subjects with generalized pustular psoriasis and erythrodermic psoriasis respectively, thus finding subjects to participate in the trial will be difficult. Therefore, the sample size is determined based on feasibility. In total, at least 16 subjects will be enrolled: at least 8 subjects for GPP and EP separately.

8.3 Randomization Methods

An IRT will be used to determine the randomization of subjects. Detailed instructions for using the IRT will be provided to the site personnel. Subjects who are eligible based on inclusion and exclusion criteria and have had all pre randomization procedures performed will be randomized in a 1:1 fashion in each group to either 150 mg (2 syringes, 75 mg each) or 75 mg (1 syringe) at Week 0, 4 and every 12 weeks. The randomization schedule will be prepared by the Statistics Department of AbbVie and provided to drug supply for adequate packaging. Randomization will be done using an adequate block size.

9.0 Ethics

9.1 Independent Ethics Committee (IEC) or Institutional Review Board (IRB)

Good Clinical Practice requires that the clinical protocol, any protocol amendments, the Investigator's Brochure, the informed consent and all other forms of subject information related to the study (e.g., advertisements used to recruit subjects) and any other necessary documents be reviewed by an IEC/IRB. The IEC/IRB will review the ethical, scientific

and medical appropriateness of the study before it is conducted. IEC/IRB approval of the protocol, informed consent and subject information and/or advertising, as relevant, will be obtained prior to the authorization of drug shipment to a study site.

Any amendments to the protocol will require IEC/IRB approval prior to implementation of any changes made to the study design. The investigator will be required to submit, maintain and archive study essential documents according to ICH GCP.

Any SAEs that meet the reporting criteria, as dictated by local regulations, will be reported to both responsible Ethics Committees and Regulatory Agencies, as required by local regulations. During the conduct of the study, the investigator should promptly provide written reports (e.g., ICH Expedited Reports, and any additional reports required by local regulations) to the IEC/IRB of any changes that affect the conduct of the study and/or increase the risk to subjects. Written documentation of the submission to the IEC/IRB should also be provided to AbbVie.

9.2 Ethical Conduct of the Study

The study will be conducted in accordance with the protocol, International Conference on Harmonization (ICH) guidelines, applicable regulations and guidelines governing clinical study conduct and the ethical principles that have their origin in the Declaration of Helsinki. Responsibilities of the clinical investigator are specified in [Appendix A](#).

9.3 Subject Information and Consent

The investigator or his/her representative will explain the nature of the study to the subject, and answer all questions regarding this study. Prior to any study-related screening procedures being performed on the subject, the informed consent statement will be reviewed and signed and dated by the subject, the person who administered the informed consent, and any other signatories according to local requirements. A copy of the informed consent form will be given to the subject and the original will be placed in the subject's medical record. An entry must also be made in the subject's dated source

documents to confirm that informed consent was obtained prior to any study-related procedures and that the subject received a signed copy.

Information regarding incentives for subjects and information regarding provisions for treating and/or compensating subjects who are harmed as a consequence of participation in the study can be found in the informed consent form.

9.3.1 Informed Consent Form and Explanatory Material

In Japan, the principal investigator will prepare the consent form and explanatory material required to obtain subject's consent to participate in the study with the cooperation of the sponsor and will revise these documents as required. The prepared or revised consent forms and explanatory material will be submitted to the sponsor. Approval of the IRB will be obtained prior to use in the study.

9.3.2 Revision of the Consent Form and Explanatory Material

In Japan, when important new information related to the subject's consent becomes available, the principal investigator will revise the consent form and explanatory material based on the information without delay and will obtain the approval of the IRB prior to use in the study. The investigator will provide the information, without delay, to each subject already participating in the study, and will confirm the intention of each subject to continue the study or not. The investigator shall also provide a further explanation using the revised form and explanatory material and shall obtain written consent from each subject of their own free will to continue participating in the study.

10.0 Source Documents and Case Report Form Completion

10.1 Source Documents

Source documents are defined as original documents, data and records. This may include hospital records, clinical and office charts, laboratory data/information, subjects' diaries or evaluation checklists, pharmacy dispensing and other records, recorded data from

automated instruments, microfiches, photographic negatives, microfilm or magnetic media, and/or x-rays. Data collected during this study must be recorded on the appropriate source documents.

The investigator(s)/institution(s) will permit study-related monitoring, audits, IEC/IRB review, and regulatory inspection(s), providing direct access to source data documents.

10.2 Case Report Forms

Case report forms (CRF) must be completed for each subject screened/enrolled in this study. These forms will be used to transmit information collected during the study to AbbVie and regulatory authorities, as applicable. The CRF data for this study are being collected with an electronic data capture (EDC) system called Rave® provided by the technology vendor Medidata Solutions Incorporated, NY, USA. The EDC system and the study-specific electronic case report forms (eCRFs) will comply with Title 21 CFR Part 11. The documentation related to the validation of the EDC system is available through the vendor, Medidata, while the validation of the study-specific eCRFs will be conducted by AbbVie and will be maintained in the Trial Master File at AbbVie.

The investigator will document subject data in his/her own subject files. These subject files will serve as source data for the study. All eCRF data required by this protocol will be recorded by investigative site personnel in the EDC system. All data entered into the eCRF will be supported by source documentation.

The investigator or an authorized member of the investigator's staff will make any necessary corrections to the eCRF. All change information, including the date and person performing the corrections, will be available via the audit trail, which is part of the EDC system. For any correction, a reason for the alteration will be provided. The eCRFs will be reviewed periodically for completeness, legibility, and acceptability by AbbVie personnel (or their representatives). AbbVie (or their representatives) will also be allowed access to all source documents pertinent to the study in order to verify eCRF entries. The

principal investigator will review the eCRFs for completeness and accuracy and provide his or her electronic signature and date to eCRFs as evidence thereof.

Medidata will provide access to the EDC system for the duration of the trial through a password-protected method of internet access. Such access will be removed from investigator sites at the end of the site's participation in the study. Data from the EDC system will be archived on appropriate data media (CD-ROM, etc.) and provided to the investigator at that time as a durable record of the site's eCRF data. It will be possible for the investigator to make paper printouts from that media.

11.0 Data Quality Assurance

Computer logic and manual checks will be created to identify items such as inconsistent study dates. Any necessary corrections will be made to the eCRF.

12.0 Use of Information

Any research that may be done using optional exploratory research samples from this study will be experimental in nature and the results will not be suitable for clinical decision making or subject management. Hence, the subject will not be informed of individual results, should analyses be performed, nor will anyone not directly involved in this research. Correspondingly, researchers will have no access to subject identifiers. Individual results will not be reported to anyone not directly involved in this research other than for regulatory purposes. Aggregate data from optional exploratory research may be provided to investigators and used in scientific publications or presented at medical conventions. Optional exploratory research information will be published or presented only in a way that does not identify any individual subject.

13.0 Completion of the Study

The investigator will conduct the study in compliance with the protocol and complete the study within the timeframe specified in the contract between the Director of the Site in Japan and AbbVie. Continuation of this study beyond this date must be mutually agreed

upon in writing by both the Director of the Site in Japan and AbbVie. The investigator will provide a final report to the IEC/IRB following conclusion of the study, and will forward a copy of this report to AbbVie or their representative.

The Director of the Site in Japan must retain any records related to the study according to local requirements. If the Director of the Site in Japan is not able to retain the records, he/she must notify AbbVie to arrange alternative archiving options.

AbbVie will select the signatory investigator from the investigators who participate in the study. Selection criteria for this investigator will include level of participation as well as significant knowledge of the clinical research, investigational drug and study protocol. The signatory investigator for the study will review and sign the final study report in accordance with the European Agency for the Evaluation of Medicinal Products (EMEA) Guidance on Investigator's Signature for Study Reports.

The end-of-study is defined as the date of the last subject's last visit.

Appendix A. Responsibilities of the Clinical Investigator

Clinical research studies sponsored by AbbVie are subject to the Good Clinical Practices (GCP) and local regulations and guidelines governing the study at the site location. In signing the Investigator Agreement in Section **14.0** of this protocol, the investigator is agreeing to the following:

1. Conducting the study in accordance with the relevant, current protocol, making changes in a protocol only after notifying AbbVie, except when necessary to protect the safety, rights or welfare of subjects.
2. Personally conducting or supervising the described investigation(s).
3. Informing all subjects, or persons used as controls, that the drugs are being used for investigational purposes and complying with the requirements relating to informed consent and ethics committees (e.g., independent ethics committee [IEC] or institutional review board [IRB]) review and approval of the protocol and amendments.
4. Reporting adverse experiences that occur in the course of the investigation(s) to AbbVie and the site director.
5. Reading the information in the Investigator's Brochure/safety material provided, including the instructions for use and the potential risks and side effects of the investigational product(s).
6. Informing all associates, colleagues, and employees assisting in the conduct of the study about their obligations in meeting the above commitments.
7. Maintaining adequate and accurate records of the conduct of the study, making those records available for inspection by representatives of AbbVie and/or the appropriate regulatory agency, and retaining all study-related documents until notification from AbbVie.
8. Maintaining records demonstrating that an ethics committee reviewed and approved the initial clinical investigation and all amendments.

9. Reporting promptly, all changes in the research activity and all unanticipated problems involving risks to human subjects or others, to the appropriate individuals (e.g., coordinating investigator, institution director) and/or directly to the ethics committees and AbbVie.
10. Following the protocol and not make any changes in the research without ethics committee approval, except where necessary to eliminate apparent immediate hazards to human subjects.

Appendix C. Study Activities

Trial Periods	Screening										Treatment										Follow-Up			
	V1	V2	V3	V4	V5	V6	V7	V8	V9	V10	V11	V12	V13	V14	V15	V16	V17	V18	V19	V20	V21			
Visit	0	4	8	12	16	22	28	34	40	46	52	64	76	88	100	112	124	136	148	160	172	184	188	
Week	-42 to -1	1	28	56	84	112	154	196	238	280	322	364	448	532	616	700	784	868	952	1036	1120	1162	1246	1274
Day																								
Visit window (days)																								
Informed consent	X																							
Demographics	X																							
Medical history	X																							
Smoking/alcohol history	X																							
Prior and ongoing medication	X																							
Psoriatic arthritis history	X																							
In-/exclusion criteria	X	X																						
Height	X																							
Weight/waist circumference ²	X																							
Physical examination ³	X ^c	X ^t	X ^t	X ^t	X ^c	X ^t	X ^t	X ^c	X ^t	X ^c														
Vital signs ⁴	X	X	X	X	X	X	X	X	X	X	X	X	X	X	X	X	X	X	X	X	X	X	X	
Adverse events	X	X	X	X	X	X	X	X	X	X	X	X	X	X	X	X	X	X	X	X	X	X	X	
Concomitant therapy	X	X	X	X	X	X	X	X	X	X	X	X	X	X	X	X	X	X	X	X	X	X	X	

Trial Periods	Screening										Treatment										Follow-Up
	V1	V2	V3	V4	V5	V6	V7	V8	V9	V10	V11	V12	V13	V14	V15	V16	V17	V18	V19	V20	V21
Visit																					
Week	0	4	8	12	16	22	28	34	40	46	52	64	76	88	100	112	124	136	148	160	172
Day	-42 to -1	1	28	56	84	112	154	196	238	280	322	364	448	532	616	700	784	868	952	1036	1120
Visit window (days)	± 3	± 7	± 7	± 7	± 7	± 7	± 7	± 7	± 7	± 7	± 7	± 7	± 7	± 7	± 7	± 7	± 7	± 7	± 7	± 7	± 7
Infection screening ⁵	X																				
Chest X-ray	X																				
Pregnancy testing ⁶	X	X	X	X	X	X	X	X	X	X	X	X	X	X	X	X	X	X	X	X	
Safety laboratory	X ^c	X ^c	X ^t	X ^c	X ^c	X ^c															
tests ⁷																					
12 lead-ECG	X																				
PK sampling ⁸	X	X	X	X	X	X	X	X	X	X	X	X	X	X	X	X	X	X	X	X	X
ADA sampling ⁸	X	X	X	X	X	X	X	X	X	X	X	X	X	X	X	X	X	X	X	X	X
Local tolerability																					
PASI	X	X	X	X	X	X	X	X	X	X	X	X	X	X	X	X	X	X	X	X	X
JDA score and responder rating	X	X	X	X	X	X	X	X	X	X	X	X	X	X	X	X	X	X	X	X	X
PGA-GPP ⁹	X	X	X	X	X	X	X	X	X	X	X	X	X	X	X	X	X	X	X	X	X
CGI-GI ¹⁰	X	X	X	X	X	X	X	X	X	X	X	X	X	X	X	X	X	X	X	X	X
DLQI																					
BSA	X	X	X	X	X	X	X	X	X	X	X	X	X	X	X	X	X	X	X	X	X
Contact IRT	X	X	X	X	X	X	X	X	X	X	X	X	X	X	X	X	X	X	X	X	X
Administration of trial drugs																					

Trial Periods	Screening										Treatment										Follow-Up			
	V1	V2	V3	V4	V5	V6	V7	V8	V9	V10	V11	V12	V13	V14	V15	V16	V17	V18	V19	V20	V21			
Visit	0	4	8	12	16	22	28	34	40	46	52	64	76	88	100	112	124	136	148	160	172	184	188	
Week	0	4	8	12	16	22	28	34	40	46	52	64	76	88	100	112	124	136	148	160	172	184	188	
Day	-42 to -1	1	28	56	84	112	154	196	238	280	322	364	448	532	616	700	784	868	952	1036	1120	1162	1246	1274
Visit window (days)	± 3	± 7	± 7	± 7	± 7	± 7	± 7	± 7	± 7	± 7	± 7	± 7	± 7	± 7	± 7	± 7	± 7	± 7	± 7	± 7	± 7	± 7	± 7	± 7
Last injection of trial medication ¹¹																								
Trial completion																								
Vital status ¹²																								

1. At Visit 1, all subjects at all sites will be evaluated via CASPAR for history of psoriatic arthritis as detailed in [Appendix F](#).
2. Refer to Section [5.3.1.1](#) for weight procedures.
3. Physical examination: C = complete, T = targeted. Refer to Section [5.3.1](#).
4. Vital signs should precede blood sampling and be assessed pre-dose at all dosing visits. At Visit 2 and Visit 3, additional vital sign assessments should be taken at 5 minutes post-dose and 60 minutes post-dose. Subjects should be closely monitored for signs and symptoms of hypersensitivity reactions for approximately 2 hours after the first dose administered and 1 hour following all other doses of study drug.
5. Infection screening consists of Hepatitis B Surface Antigen (qualitative), Total Hepatitis B Core Antibodies (qualitative), Hepatitis B Surface Antibody (qualitative), Total Hepatitis C Virus RNA (Quantitative) reflex, Hepatitis C Virus RNA (Qualitative), Hepatitis C Antibodies (Qualitative), Hepatitis C Antibody (Qualitative), PPD or Quantiferon-TB. Hepatitis B, Hepatitis C and HIV testing will be performed at screening, Visit 12, 16, 20 and Week 184.
6. Serum pregnancy testing in all female subjects at screening and if urine pregnancy test is positive. Urine pregnancy testing will be done in women of child-bearing potential prior to administration of study drug at all dosing visits and at each Follow-Up Visit.
7. C = complete, T = targeted. Targeted lab samples should be limited to WBC, serum CRP and serum albumin for the measurement of JDA. Subjects should be fasting for at least 8 hours prior to the blood sample being taken at the "complete" visits, except for screening. If not fasted mark on laboratory requisition form.
8. On dosing visits, PK and ADA sampling should be taken approximately within 1 hour prior to administration of study drug.
9. Collected for Substudy GPP.
10. Collected for Substudy EP.

11. Subjects that terminate trial medication early will complete EOT Visit procedures instead of the planned treatment period visit and return for Week 188 Follow-up Visit, 16 weeks after last dose of study medication.
12. Vital Status should be collected for subjects leaving the study before the planned Week 188 Follow-up visit.

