Visits 2, 4, 6, 8, 10, 12, 16, 20, end of treatment (EOT), Week 184 follow-up visit and Week 188 follow-up visit will be performed in fasted state (8 hours no food and only water). If a subject comes in non-fasted where a fasting condition is required, the visit should be performed, the non-fasted condition documented on the laboratory requisition, and the subject reminded about the expected conditions. At Visits 3, 5, 7, 9, 11, 13, 14, 15, 17, 18, 19, 21, only white blood cell count (WBC), serum C-reactive protein (CRP) and serum albumin ("targeted" lab) will be collected and fasting is not required for these labs.

Urine pregnancy testing for all woman of child-bearing potential will be conducted on-site prior to every dosing and must be negative to further treat the subject. A positive urine test must be confirmed with a serum pregnancy test.

Randomization via IRT and administration of study medication should be the last activity at Visit 2.

Venipuncture (i.e., safety laboratories, PK, anti-drug antibody [ADA]), should be the last procedure prior to study drug administration.

Follow Up Period and Trial Completion

For all randomized subjects termination of trial medication and trial completion must be recorded on the corresponding eCRFs.

Early Treatment and Trial Termination

Subjects who prematurely discontinue (PD) treatment prior to the planned [Appendix C](#) visit schedule will complete EOT visit procedures instead of the planned treatment period

visit. If study medication is discontinued, every effort should be made to have the subject continue in the trial and complete all of the follow remaining trial and follow up visits. If a subject cannot or will not continue in the trial, these subjects should be registered as withdrawn/discontinued in IRT. These subjects should be registered as withdrawn in IRT and return to the clinic for Week 188 Follow-Up visit 16 weeks after last dose of study medication.

Trial Completion

Subjects who finish the randomized treatment period will return to the clinic for Week 184 Follow-Up Visit and Week 188 Follow-Up Visit. Completion is defined as a subject having completed the Week 188 Follow-Up visit.

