5.2.3.2 Rescue Therapy

There are no special emergency procedures to be followed.

In the event that a subject experiences an intolerable worsening of GPP or EP, as deemed by the investigator, during the course of the trial the subject will be discontinued from the trial to receive rescue treatment.

In case of adverse events in need of treatment, symptomatic therapy according to investigator judgment will be permitted. All concomitant and/or rescue therapies will be recorded on the appropriate pages of the eCRF.

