- If a subject experiences an intolerable increase of psoriasis during the course of the trial the subject will be discontinued from the trial to receive rescue treatment as deemed appropriate by the investigator
- The subject has repeatedly shown to be non-compliant with important trial procedures and, in the opinion of the investigator, is not willing or able to stick to the trial requirements in the future.

Discontinuation of study medication should not lead to withdrawal from the study. If possible the subject should complete all study visits and procedures as initially planned.

Given the subject's agreement, the subject will undergo the procedures for premature discontinuation and follow up as outlined in [Appendix C](#). If a subject becomes pregnant, refer to Section [6.1.6](#) for instructions on treatment termination.

For all subjects the reason for withdrawal (e.g., AE) must be recorded in the eCRF. These data will be included in the trial database and reported.

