5.5 Treatments

5.5.1 Treatments Administered

Subjects in each group will receive either 150 mg or 75 mg of risankizumab at Week 0, 4 and every 12 weeks after. All products will be supplied by BI.

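### Appendix C note 11 gives every early drug stopper a two-visit exit while Sections 5.1 and 5.4.1 keep them in the trial, so Week 16 and Week 52 response is imputed or observed depending on the passage followed

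*Protocol*

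**What the plan says.** Three places in the protocol tell a site what to do when a subject stops study drug early.

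- **Appendix C, note 11:** "Subjects that terminate trial medication early will complete EOT Visit procedures instead of the planned treatment period visit and return for Week 188 Follow-up". That return is timed 16 weeks after the last dose. The note covers anyone who stops drug and mentions no other visit.
- **Section 5.1, Early Treatment and Trial Termination:** after the EOT procedures, every effort is to be made to "have the subject continue in the trial and complete all of the follow remaining trial and follow up visits". A separate group follows: "If a subject cannot or will not continue in the trial, these subjects should be registered as withdrawn/discontinued in IRT". The single return 16 weeks after last dose is given to that group.
- **Section 5.4.1:** stopping drug should not mean leaving the study, and "If possible the subject should complete all study visits and procedures as initially planned". The next paragraph then says that, if the subject agrees, "the subject will undergo the procedures for premature discontinuation and follow up as outlined in" Appendix C.

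Section 5.1 also states: "Completion is defined as a subject having completed the Week 188 Follow-Up visit". Subjects who need rescue are a separate matter, because under Section 5.2.3.2 "the subject will be discontinued from the trial to receive rescue treatment".

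SAP Section 6.0 imputes a missing binary response as failure when nothing is assessed afterwards. When there are assessments on both sides, it imputes success only if both are successes. Visits after the start of prohibited psoriasis medication count as failures. Missing continuous values are carried forward. No rule makes stopping study drug a failure in itself.

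**The concern.** Note 11 applies to all drug stoppers the path that Section 5.1 reserves for those who leave. It calls the 16-week return the Week 188 visit, which is the visit that defines completion, so a site will naturally read it as the last one. A subject who stops at Week 12 and returns 16 weeks after the Week 4 dose could even be recorded as a completer. Because 5.4.1 sends the reader to Appendix C, the footnote may well be the instruction that is followed.

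The primary endpoint is exposed because of the dosing schedule: "Subjects in each group will receive either 150 mg or 75 mg of risankizumab at Week 0, 4 and every 12 weeks after". The only doses due before the Week 16 evaluation are at Weeks 0 and 4. A subject who stops at Week 8 or 12 has received both, and the Week 16 outcome still says something about the assigned regimen. Whether it is observed or imputed should not depend on which page the site opened. The same applies to Week 52 response, which is secondary. No hypothesis is tested, so the counts in very small arms are the efficacy evidence.

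**Working it through.** **Inputs.** Doses fall at Weeks 0, 4, 16, 28 and 40 (Protocol 5.5.1). The SAP Table 1 windows are Rx Days 100 to 134 for Week 16 and 345 to 407 for Week 52. There are at least 8 subjects per substudy, randomized 1:1 (Protocol 8.2 and 5.5.3), so about 4 per arm. The plan has no figure of its own to reproduce on this point.

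**Step 1: place the note 11 visits.** EOT takes the place of the planned visit at the stop week.

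- EOT Rx Day = 7 × stop week + 1
- Return Rx Day = 7 × (last dose week + 16) + 1

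Example, stop at Week 12: EOT = 7 × 12 + 1 = 85; return = 7 × (4 + 16) + 1 = 141.

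| Stop week | Last dose week | EOT day | Return day (window) | Week 16 window filled | Week 52 window filled |
|---|---|---|---|---|---|
| 4 | 0 | 29 | 113 (Week 16) | only if efficacy is done at the return | no |
| 8 | 4 | 57 | 141 (Week 22) | no | no |
| 12 | 4 | 85 | 141 (Week 22) | no | no |
| 16, before dosing | 4 | 113 | 141 (Week 22) | yes | no |
| 22 | 16 | 155 | 225 (Week 34) | yes | no |
| 28 | 16 | 197 | 225 (Week 34) | yes | no |
| 34 | 28 | 239 | 309 (Week 46) | yes | no |
| 40 | 28 | 281 | 309 (Week 46) | yes | no |
| 46 | 40 | 323 | 393 (Week 52) | yes | only if efficacy is done at the return |

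The Week 16 window is empty for stops at Weeks 8 and 12. The Week 52 window is empty for all eight stop visits from Week 4 to Week 40.

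**Step 2: apply the SAP rules.** For a Week 8 or 12 stop, Week 16 response is a failure if no efficacy is collected at the Day 141 return. If it is collected, the before-and-after rule applies and can give success. For the eight stops from Week 4 to Week 40, nothing follows the Week 52 window, so the result is failure. Under 5.1 both values are observed if the subject attends, unless prohibited psoriasis medication has been started, which is a failure on either route.

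**Step 3: count visits for a Week 12 stop.** Note 11 gives 2: EOT and the return. Section 5.1 gives EOT plus up to 19: Weeks 16, 22, 28, 34, 40, 46, 52, then 64 to 172 (10 visits), 184 and 188.

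**Step 4: what one subject is worth.** In an arm of 4, 1/4 = 25 percentage points. The SAP plans 95% intervals for percentages without naming a method; exact (Clopper-Pearson) limits are assumed here.

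- Observed as a responder: 4/4 = 100% (39.8 to 100)
- Imputed as failure: 3/4 = 75% (19.4 to 99.4)

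Over a substudy of 8 the shift is 12.5 points: 8/8 (63.1 to 100) against 7/8 (47.3 to 99.7).

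**Step 5: chance of meeting the problem.** The documents give no early-stop rate. For an assumed per-subject probability p of an early stop at any time, the chance of at least one among 16 is 1 − (1 − p)^16: 27.6% for p = 2%, 56.0% for 5%, 81.5% for 10%. For a stop at Week 8 or 12 only, assume stops spread evenly over the 19 visits from Week 4 to Week 160 and replace p by 2p/19. This gives about 3%, 8% and 16%.

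**The case against.** The best defence is that note 11 never says visits end. It can be read as a shortened form of the 5.1 paragraph, and the 5.4.1 pointer may mean the EOT/PD and follow-up columns of the schedule rather than this footnote. The two instructions can also be combined, as the fix below does. This reading is possible but weak. Note 12, directly below, speaks of subjects leaving the study, whereas note 11 speaks of those who stop medication, so the two groups are worded differently side by side.

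Several limits on the impact do stand:

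- The Week 16 effect needs a stop at Week 8 or 12, neither of them a dosing visit, without rescue or prohibited medication, in someone willing to keep attending.
- A return 7 days early, on Day 134, would fall inside the Week 16 window. The Week 52 gap does not close that way: the latest affected return, Day 309, is Day 316 even if 7 days late.
- SAP Table 1 has a Week 188 window for the efficacy variables. If efficacy is collected at the return, a subject responding on both sides is imputed as a success, so 3/4 against 4/4 is the worst case.
- Someone who stops by Week 40 had the last dose at Week 28 or earlier, so is at least 52 − 28 = 24 weeks past it at Week 52. Many may by then have failed on either route through prohibited medication, or left for rescue. The documents do not allow the remainder to be sized.
- Sections 5.1 and 5.4.1 are best-effort wording, so observation is not guaranteed.

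The plan also includes as-observed analyses (Protocol 8.1.9, SAP 10.1). These would show 3/3 beside 3/4, which discloses the gap but does not recover the missing outcome.

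**Conclusion.** The concern holds. Note 11 conflicts with Sections 5.1 and 5.4.1 for subjects who stop drug without needing rescue, and the passage followed decides whether their Week 16 or Week 52 response is observed or imputed. The effect on the primary endpoint is narrow (stops at Weeks 8 and 12); the effect on Week 52 response is broad (eight stop visits). One affected subject can move an arm of about 4 by up to 25 percentage points. This rests on visits at nominal days, on the subject being willing to attend, and on exact intervals. The early-stop probabilities are illustrations, not estimates. It should be corrected: it is a drafting conflict with a real effect on endpoint data, and the correction is small.

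**What to change.** Reword note 11 along these lines: *A subject who stops study drug early has the EOT procedures at that visit. Every effort is then made to have the subject attend each remaining scheduled visit without dosing, and safety assessments, including a urine pregnancy test where applicable, are done 16 weeks after the last dose. A subject who leaves the study has only the Week 188 Follow-Up Visit, timed 16 weeks after the last dose.* The pointer in 5.4.1 then agrees with the rest.

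The 16-week visit is worth keeping for stayers. Contraception runs to 16 weeks after last dose (5.2.4), while urine tests are tied in the text to dosing and follow-up visits (5.3.1.1). Without it, the next test named in the text after a Week 12 stop is at Week 184. The Appendix C pregnancy row is not legible enough to confirm that gap.

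The change is one footnote, made by protocol amendment with the ethics approval that Section 9.1 requires, and no SAP change. The remaining visits are already requested in 5.1 and 5.4.1. A subject who stays attends at most one visit more than under 5.1 alone.
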